Annex 6 – Infusion protocol

Form Version 1 Printed from StemCare QMS 2019-01-22 Page 1 of 1 CBU Infusion Procedures

Principle

At the transplant center, the cryoprotected cord blood unit (CBU) is stored in the vapor phase of liquid nitrogen until the day of transplant, when it is thawed and washed in dextran / albumin, a process which increases cell viability and removes approximately 90% of the DMSO/dextran cryoprotectant. The washed cells are resuspended in dextran/albumin and transported to the patient's bedside in a labelled transplant bag for infusion.

The unit is infused into the patient's blood via the central venous catheter over 2-30 minutes. Every effort should be made to be sure that all the cells in the transplant bag and IV tubing are delivered to the patient, maintaining a closed system during the infusion.

Specimen

Thawed and washed cells from a cryopreserved cord blood unit (CBU) in a labelled transplant bag.

Reagents

500 ml bag of Normal Saline

Supplies

Y-infusion set

IV extension tubing

Blood filter, 170-260 microns

Procedure

- 1. Verify that the patient is stable and has received premeds for transplant.**
- 2. Verify that the transplant bag label matches patient identifiers via institutional procedures.**
- 3. Examine transplant bag to be sure that cells are in solution and that large clumps are not present in the bag. If clumps are present, prepare to use blood filter in infusion set-up.**
- 4. Close all clamps on the tubing on the Y-infusion set and blood filter.**
- 5. Spike one arm of the Y-infusion set into the bag of normal saline.**
- 6. Connect extension tubing to the distal arm of the Y-infusion set.**
- 7. Prime all tubing with normal saline.**

- 8. Spike the other arm of the Y-infusion set into the transplant bag.**
- 9. Connect the distal end of the extension tubing to the patient's central venous catheter.**
- 10. Open the clamps between the transplant bag, the extension tubing, and the patient's central line and allow cells to infuse into the patient's blood.**
- 11. Rinse residual cells in the transplant bag and tubing. After all cells have dripped out of the transplant bag, close the clamps on the extension tubing and Y-set connected to the transplant bag. Open the clamps between the normal saline bag and transplant bag and allow approximately 25 cc of saline to run into the transplant bag. Close the clamps between
the saline bag and transplant bag and open the clamps between the transplant bag and the patient and infuse this saline to the patient. Repeat rinse x 1.**
- 12. Monitor the patient's vital signs before, during and after infusion per institution**

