3 STUDY PLAN AND PROCEDURES

3.1 Study design

This is a twelve months long, open-label, crossover study to evaluate the comparative efficacy and safety of UCB versus non-invasive treatments in children with ASD. Each participant will receive both treatments in a random sequence.

The UCB is autologous, previously harvested at the child's birth and cryopreserved in liquid nitrogen for later use.

The UCB infusion was performed at Angiomedica Hospital, [name] as main site and in two additional clinical sites: Medicover Hospital, [name], and Ponderas Academic Hospital, [name], all in Bucharest, Romania by anesthesiologist and pediatric physician, based on the Duke protocol.

Prior to UCB infusion, HLA typing of the child will be performed at the National Institute of Hematology, as well as the HLA typing of the UCB prior to thawing – for positive identification. During this time the UCB collection will be kept in liquid nitrogen for a maximum of 72 hours, after which thawing and preparing of the UCB for infusion will be performed by [name]; the thawing is done in optimal conditions for preserving simultaneously both sterility and viability of the cryogenated cells - the Vita 34 or Rubinstein protocols; testing for viability will be done with Trypan Blue and flowcytometry. Choosing optimal conditions is based upon the minimum number of processing steps necessary (fewest number of centrifugations and shortest time of processing, with best recovery of various stem cells) and ensuring sterility.

The non-invasive treatment combination is prescribed by the study investigator after the three questionnaires are answered and an evaluation by child therapist/psychologist is performed independently. This treatment is

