15. If you or someone else in the family is visibly upset, does your child show signs of wanting to comfort them (e.g. stroking their hair, hugging them)?
- always
 - usually
 - sometimes
 - rarely
 - never

16. Does your child do the same thing over and over again (e.g. running the tap, turning the light switch on and off, opening and closing doors)?

- many times a day
- a few times a day
- a few times a week
- less than once a week
- never

17. Would you describe your child's first words as:

- very typical
- quite typical
- slightly unusual
- very unusual
- my child doesn't speak

18. Does your child echo things s/he hears (e.g. things that you say, lines from songs or movies, sounds)?

- many times a day
- a few times a day
- a few times a week
- less than once a week
- never

19. Does your child use simple gestures (e.g. wave goodbye)?

- many times a day
- a few times a day
- a few times a week
- less than once a week
- never

20. Does your child make unusual finger movements near his/her eyes?

- many times a day
- a few times a day
- a few times a week
- less than once a week
- never

21. Does your child spontaneously look at your face to check your reaction when faced with something unfamiliar?

- always
- usually
- sometimes
- rarely
- never

22. How long can your child's interest be maintained by just one or two objects?

- most of the day
- several hours
- half an hour
- ten minutes
- a couple of minutes

23. Does your child twiddle objects repetitively (e.g. pieces of string)?

- many times a day
- a few times a day
- a few times a week
- less than once a week
- never

24. Does your child seem oversensitive to noise?

- always
- usually
- sometimes
- rarely
- never

25. Does your child stare at nothing with no apparent purpose?

- many times a day
- a few times a day
- a few times a week
- less than once a week
- never

Annex 5

**UCB thawing protocol (adapted from Duke/Rubinstein protocols and Vita 34)
Form FL.03.01.07, Version 1 Printed from StemCare QMS 2019-01-22**

CBU Thawing Procedures

Principles

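### Annex 6, the only infusion procedure supplied, is written for a transplant recipient with a central line and unnamed premedication, not for children aged 3 to 7 with ASD

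*Combined protocol and SAP*

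**What the plan says.** Annex 6 carries the title of infusion protocol and the form header "Form Version 1 Printed from StemCare QMS 2019-01-22 Page 1 of 1 CBU Infusion Procedures". Its Principle states: "The unit is infused into the patient's blood via the central venous catheter over 2-30 minutes". The procedure then repeats the route twice. Step 9 reads "Connect the distal end of the extension tubing to the patient's central venous catheter" and step 10 reads "Open the clamps between the transplant bag, the extension tubing, and the patient's central line and allow cells to infuse into the patient's blood". Step 1 sets a precondition: "Verify that the patient is stable and has received premeds for transplant". No drug, dose or timing is given there or elsewhere in the text supplied.

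The body of the protocol says much less. The synopsis describes treatment A as autologous cord blood given intravenously, once. Section 3.1 says that the infusion is done "by anesthesiologist and pediatric physician, based on the Duke protocol", at one hospital "as main site and in two additional clinical sites". Section 4.2 records for Visit 1 only that the infusion takes place. Section 3.3.5 prefers that no other medicine be taken and asks that incidental medication be recorded; it names no premedication for the infusion. The Duke infusion procedure is not reproduced, and no section of the body refers to Annex 6.

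**The concern.** The annex is the only place where a clinical team can read how to give treatment A, and its wording belongs to another kind of patient: someone on the day of a transplant who already has a central line and has had transplant premedication. The trial enrols children aged 3 to 7 with ASD for a single infusion of their own cord blood.

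Two things are at stake. The first is patient safety: a literal reading leads to central venous access and unspecified drugs in a young child, and the protocol gives no reason for either. The second is the definition of treatment A. Comparing the two safety profiles is the secondary objective (section 2), and adverse events head the safety endpoints (section 4.1). Events caused by venous access or premedication properly count under treatment A, but that profile is harder to interpret if the plan does not fix the route and the drugs.

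**Working it through.** The protocol states no figure on this point, so the check is a comparison of texts.

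| Item | Annex 6 | Body of the protocol |
|---|---|---|
| Venous access | Central, in the Principle and steps 9 and 10; no peripheral option | Intravenous, not further specified (synopsis) |
| Premedication | Required by step 1; no drug, dose or timing | None named (4.2, Visit 1; 3.3.5) |
| Patient and setting | Transplant center, day of transplant, transplant bag; neither children nor ASD mentioned | Children aged 3 to 7 with ASD (3.2, 3.2.1) |
| Stated source | None beyond the form header | Duke protocol (3.1), not supplied |

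1. **Number of issues.** The Principle, step 9 and step 10 give one instruction three times. Step 1 gives a second. There are two issues, access and premedication, located in one paragraph and three of the twelve numbered steps.

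2. **Can the annex be followed as written in these children?** Step 9 connects the tubing to a catheter that the patient is assumed to have. No inclusion criterion, visit procedure or treatment section says that a participant has one. The Supplies list contains an infusion set, extension tubing and a filter, but nothing for placing a line. For a child without a central line, the team must therefore either place one or depart from the annex.

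3. **Can step 1 be satisfied?** It requires confirmation that premedication has been given. With no drug named, the treating team must choose one or skip the step. Dose matters, because the permitted body weight spans a factor of 30/15 = 2 under section 3.2.1, or 30/10 = 3 under the synopsis.

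4. **Does another section resolve this?** Section 3.1 names the Duke protocol as the basis but does not say whether Annex 6 is that procedure, an adaptation of it or something separate. The heading of Annex 5 does state its sources, beginning "UCB thawing protocol (adapted from Duke"; Annex 6 has no comparable line.

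5. **Exposure bounds.** There is one infusion per child (synopsis). Section 3.2 requires at least 25 children to receive both treatments, and the synopsis gives 40 as the optimum. If the annex were followed literally throughout, 1 × 25 = 25 to 1 × 40 = 40 children would be affected; if it were followed nowhere, 0. These are bounds only. The documents give no basis for placing the true number between them.

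**The case against.** The strongest reply is that this is a wording gap with no shown consequence. Several parts of that reply stand.

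- **The annex does not order a line to be inserted.** It presupposes one, and an anesthesiologist takes part in the infusion. This is correct. A reader might infer that the plan instructs catheterisation of every child, and the text does not go that far. What remains is that the only access described is central, for patients who are not said to have such access.
- **One basis is named for all three hospitals.** Section 3.1 covers them in a single sentence. A reader might infer that the sites would use different procedures; that is speculation against the stated text. Only the link between that basis and Annex 6 is missing.
- **Central infusion is still intravenous.** So the annex and the synopsis do not contradict each other.
- **The Duke procedure has not been seen.** It may specify peripheral access, central access or particular premedication. The documents cannot show that Annex 6 departs from it.
- **The form's origin proves little.** Annex 5 carries the same StemCare print date and uses transplant vocabulary too, yet is labelled as adapted in part from Duke. A reader might infer from the header that Annex 6 is foreign to the trial, or that it is a cord-blood bank's form. The documents do not say what StemCare is, and the header does not settle the matter.
- **The criterion of no regular medical treatment** concerns eligibility. It does not bear on venous access or on a one-off procedural drug.
- **The data would help to show problems.** Adverse events are listed individually by treatment group (5.2) and incidental medication is recorded (3.3.5).

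The consent form and the investigator's file were not available and may describe the intended route. That could change what happens in practice, but not what Annex 6 tells its reader to do.

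**Conclusion.** The point holds as a patient-safety defect in a supplied instruction, of minor to moderate severity. It is more than missing detail, because the annex positively states an access route and a precondition that do not suit the participants, and the protocol justifies neither.

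It should not be read as evidence that any child received a central line or transplant premedication, for the documents do not show what was done. It has no bearing on the efficacy comparison or on the planned analysis.

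The conclusion rests on two assumptions: that participants do not generally arrive with a central line, which the protocol nowhere suggests, and that peripheral access is adequate for a single infusion in most of them. The second is a clinical judgement that the documents neither state nor exclude, which is why the amendment should leave room for a documented exception.

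**What to change.** Three edits are enough.

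- In Annex 6, change the Principle and steps 9 and 10 to peripheral intravenous access, with a central line only where the anesthesiologist documents a need for it in that child.
- In step 1, delete the transplant premedication or replace it with the named drugs and weight-based doses to be used.
- In section 3.1, add one sentence stating that the amended Annex 6 is the infusion procedure used at all three hospitals.

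The cost is a revised one-page annex, one sentence in the body and an amendment notice under section 5.3. No patients, visits or procedures are added. Section 3.1 describes infusions in the past tense, so for any already given the study report should state the access route and premedication actually used.
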